5.3 Exploratory endpoints

- Pressure measurement at first flow-stop derived from a catheterisation profile, [mbar]

[figure not shown]

Figure 5-2 Overview of measurements during and after catheterisation.

Microtrauma: Concentration of microscopic haematuria and incidences of positive haematuria indicates possible catheter-associated microtrauma. With the micro-hole zone catheter, fewer mucosal suctions and putatively less or no co-sequential blood in the urine is expected. This is based on previous literature showing mucosal suction and associated trauma with indwelling catheters (Glahn, 1988; Glahn et al., 1988; Grocela & Jura, 2010; Milles, 1965), which has also been demonstrated with conventional 2-eyelet intermittent catheters in the preclinical setting (Coloplast A/S, 2021b, 2021c) (data not yet published).

5.6 Demography and potential compromising factors

The following baseline data will be collected and registered at visit 1(V1) by the investigator or designee:

- Date of informed consent
- Date of visit
- Age
- When did you start using a catheter? (months or years)
- Average number of catheters used per day during the last month
- Current device brand/type (can choose more than one)
 - Braun Actreen
 - Bard
 - Bullens
 - CliniMed
 - Coloplast
 - Convatec
 - Cure
 - Hollister
 - Manfred Sauer
 - TeleFlex
 - Wellspect
 - Oasis
 - LentisMed

- Second sequence: The comparator, then the investigational device.

Randomisation will be centralized using Medidata RAVE, see section 11.

5.9 Total expected duration of the clinical investigation

The dates below are approximate, and no subjects will be enrolled before all required approvals have been obtained. If changes are required, applicable IRB/EC and regulatory authorities will be notified.

First patient in (FPI)	July 2022
Last patient in (LPI)	October 2022
Last patient out (LPO)	October 2022
Database lock (DBL)	November 2022

6 Clinical Investigation population

The clinical investigation will be conducted in 42 subjects enrolled in 1-3 clinical investigation sites in Denmark and USA.

6.1 Eligibility criteria

To be included in the investigation, the subjects must comply with the selection criteria described below

6.1.1 Inclusion criteria

For a subject to be eligible, all inclusion criteria must be answered "yes":

Inclusion criteria	Justification for inclusion criteria
1. Is Male	Intended patient population of investigational and comparator devices.
2. Is at least 18 years of age and has full legal capacity	Intended patient population of investigational and comparator devices. To meet Helsinki Declaration.
3. Has given written informed consent	To ensure that the subject has been given written and oral information regarding the investigation and know enough about the investigation to decide on participation. To ensure voluntariness and that Helsinki Declaration is met.
4. Has signed letter of authority (only DK)	Letter of Authority is a demand from Danish Medicines Authorities.
5. Has used clean intermittent catheterisation CH12 or CH14 for at least one month	To ensure that the subject is used to catheterization.
6. Use intermittent catheterisation as the primary bladder emptying method	To ensure that the subject is used to catheterization.
7. Is able (assessed by investigator) and willing to follow study procedures	To ensure sufficient data for successful completion of the study.

6.1.2 Exclusion criteria

For an eligible subject, all exclusion criteria must be answered "no":

Exclusion criteria	Justification for exclusion criteria
1. Is participating in any other clinical study during this investigation	To eliminate uncertainty whether any Adverse Events (AE's) or Serious Adverse Events (SAE's) occurring during the investigation relate to use of the herein tested devices. Also, to eliminate unintentional effect from other devices/medicines on the investigation's data.
2. Has previous participated in this study	To ensure integrity of results.
3. Has symptoms of urinary tract infection as judged by the investigator	To ensure subject safety and integrity of results.

'recruitment landing page'. CROs will assist by receiving 'reply to' letters-mails and/or answering the phone from interested subjects.

6.2.5 Coloplast database

If needed, recruitment of subjects can also go through Coloplast's own subject database (intermittent catheter users) or by advertisements in e.g., local newspapers or relevant associations newspapers. The advertisement letter will include the contact information of the investigator or delegated study personnel (address, phone number and email address).

In the Coloplast database, potential subjects are identified by the following search criteria: subjects who have consented to be contacted for future clinical investigations and e.g., intermittent catheter user, male and at least 18 years of age and diagnose. The identified potential subjects will as first contact be sent the advertisement letter by mail or email. The advertisement letter includes the contact information of the investigator or delegated study personnel (address, phone number and email address).

6.3 Subject withdrawal criteria

The subject is allowed to withdraw from the investigation at any time for whatever reason without any consequences for their future treatment outside the clinical investigation. The Investigator may withdraw a subject from the investigation at any time if they judge it to be the subject's interest.

The investigator must withdraw a subject from the investigation due to:

- Noncompliance with the CIP impacting the scientific integrity of the investigation.
- If subject's safety and wellbeing is compromised by further participation.
- Subjects lost to follow-up. At least three documented attempts will be made to verify subjects lost to follow-up.

Randomized subjects that for some reason withdraw from the clinical investigation can be replaced. Replacements should be discussed with Sponsor. Please also refer to section 10.2 Sample size for further information.

6.4 Point of enrolment

A subject is considered enrolled in the investigation at the time at which, following recruitment and before any clinical investigation-related procedures are undertaken, the subject signs and dates the informed consent form.

6.5 Subject Identification and Confidentiality

Subjects will be identified on the electronic CRF (eCRF) and any other document transmitted to the sponsor by the principal investigator or clinical site staff, by a unique identification number.

Data entered on the eCRF are confidential and will only be available to the sponsor (including sponsor delegates), members of data management teams, the statistician, members of the EC or IRB and if requested to regulatory authorities.

The principal investigator for each clinical investigation site will maintain as part of the investigational file a list identifying all subjects entered into the clinical investigation.

7 Procedures

7.1 Clinical investigation-related procedures

Visit 0 (V0) - Screening:

- Subject is informed about the study and screened for eligibility.

Visit 1 (V1):

- Informed consent obtained
- Check of inclusion and exclusion criteria

Concomitant medication potentially affecting urinary function (assessed by investigator)	Investigator/delegate		X	X
Relevant medical history	Investigator/delegate		X	
Randomization	Investigator/delegate		X	
Pre-catheterization volume measured 3 times with bladder scanner: - The test can only proceed after 3 consecutive measurements above 150 ml - If below 150 ml, subjects are required to drink at least 500 ml fluids for the next hour, and then measurements are retaken	Investigator/delegate		X	X
Registration/measurement of end points				
Catheterisation measuring sensor profile	Investigator/delegate		X	X
Urine volume at 1 st flow stop	Investigator/delegate		X	X
Urine volume measured post catheterisation	Investigator/delegate		X	X
Post-catheterization residual volume measured 3 times with a bladder scanner	Investigator/delegate		X	X
Dipstick test for haematuria (post catheterisation)	Investigator/delegate		X	X
AEs/ADEs/SAEs/SADEs/DDs	Investigator/delegate		X	X
Termination form	Investigator/delegate			X

7.3 Case Report Forms

All assessments and observations throughout the investigation for each subject must be carefully recorded in an electronic CRF (eCRF).

CRFs will be filled in by the investigator and/or delegated site personal, who have signed the Site Personnel Signature and Delegation List and Clinical Investigation Training Log. The delegated site personal will be required to complete e-learning prior to system access. Delegated personal will receive credentials.

It is the responsibility of the Investigator that all data are entered promptly and correctly.

7.4 Concomitant treatment

Concomitant medication, potentially affecting urinary function (assessed by investigator), taken from the time of consent through the study, until termination will be registered in the eCRF in the concomitant medication section.

To the extent possible – the subjects should not have changed their medication the last 24 hours before visit 1 and 2. Any changes in medicine potentially affecting urinary function (assessed by investigator), should be recorded under concomitant medication.

event or serious adverse event (how, when, to whom), and who to contact in case of emergency related to the investigational device.

9 Monitoring Plan

The sponsor is responsible for ensuring appropriate monitoring of the clinical investigation activities.

The monitors will be the primary contact for the principal investigator and clinical investigation site personnel.

Monitoring activities are mandatory as per good clinical practice, however the extend and depth of these activities depend on the criticality of the clinical investigation, speed of enrolment, the experience of the clinical investigation site personnel in carrying out clinical investigations and specific study designs.

For the purpose of this clinical investigation the below described monitoring procedures have been determined.

9.1.1 Site selection visit

Depending on the prospective clinical investigation sites experience with the specific investigational device, an on-site qualification or site selection visit shall be performed during which the feasibility of the clinical investigation requirements will be discussed and common agreement between sponsor and principal investigator shall be reached. This visit may also be replaced by one or more phone calls if the principal investigator is known to the sponsor.

9.1.2 Initiation visit

All clinical investigation sites will complete an initiation visit during which full training on all aspects of the clinical investigation will be provided.

Training in use of the equipment used for measuring endpoints will be performed at sites.

9.1.3 Monitoring visit(s)

The sponsor shall determine the extent and nature of monitoring appropriate for the clinical investigation based on the risk assessment. The sponsor shall ensure, through oversight of the clinical investigation and timely adverse event reporting, that unanticipated adverse device effects are identified and investigated rapidly so that, where necessary, additional risk control measures can be implemented.

The site dedicated monitor is to ensure adherence to the clinical investigation plan, the safety of the subjects, accurate data recording on the e-CRFs and to monitor recruitment rates and adherence to follow-up schedules. During the clinical investigation, monitors shall check that appropriate written informed consents have been obtained. The Principal investigator shall permit and assist the monitor to carry out verification of completed e-CRFs against data in the source documents.

The principal investigator can delegate tasks to his/her collaborators, however the roles and responsibilities as time period of involvement for each clinical site personnel must be documented on the Site Personnel signature and Delegation list as well as training received before getting involved with the clinical investigation must be documented in the Clinical Investigation Training Log.

The monitor shall inform the sponsor about any problems relating to facilities, technical equipment or medical staff at the clinical investigation site. The monitor shall also be responsible for notifying such deficiencies in writing to the principal investigator and convene with the clinical investigation site personnel appropriate and timely corrective actions.

The sponsor, or delegate, will provide clinical monitoring, including review of eCRF with verification to the source documentation.

The monitor shall make written reports to the sponsor, including documentation of any deviations after each visit and provide written follow up action items if any, to the principal investigator and/or clinical investigation site personnel.

Baseline assessments and endpoints will be reported by descriptive statistics and/or listed. Summaries will be presented by device i.e., investigational or comparator device and if relevant, by other grouping variables.

Descriptive statistics for continuous variables are presented with N, Mean, SD (standard deviation), Median, Min and Max, where N denotes the number of subjects contributing with non-missing data. For discrete variables, descriptive statistics are presented with N and percentage, where percentage is based on the total number of subjects/observations with non-missing data.

All statistical analysis will be performed with SAS (version 6.4/Enterprise Guide version 7.1).

10.2 Definition of analysis populations

Screening Failures (SF), Intention to Treat (ITT), Full Analysis Set (FAS), Safety and Per Protocol (PP) analysis set will be defined at a formal data review meeting prior to database lock. As a minimum, the data manager, the clinical manager, and the statistician will be involved in the classification of subjects.

Subjects not adhering to inclusion and/or exclusion criteria are considered screening failures (SF) and are not randomised.

The Safety population will constitute all subjects enrolled i.e., subjects who have given informed consent.

The ITT population will constitute all randomised subjects.

The full analysis set is a modified ITT population i.e., a sub-population of the ITT population, and will constitute all randomised subjects, who have been exposed to at least one device, with at least one endpoint recorded (data non-missing).

The PP is a sub-population of the full analysis set where all subjects have received treatment as per protocol.

Individual endpoints/data points may be excluded from the analysis, even though the corresponding subject belongs to any of the pre-defined populations. Exclusion of subjects or data points must be documented.

All statistical analysis and test of hypothesis will be based on the full analysis set, and in addition, Primary and Secondary endpoints will also be analysed in the PP population, if the PP population differs from the full analysis set. whereas adverse events and device deficiencies will be assessed in the safety population.

10.3 Multiplicity control and adjustment of error probabilities

The family-wise Type I error rate will be controlled in a hierarchical fashion in support of demonstrating superiority of the investigational device.

The primary endpoints will be evaluated in a fixed sequence, where the first null-hypothesis must be rejected at a 5% significance level (alpha 0.05) before proceeding with the next.

10.4 Analysis of the primary endpoints

- Residual volume at first flow-stop, will be analysed in a general linear mixed model with subject included as a random component. Evidence of superior effect will be concluded, if the 95% confidence interval of the difference between comparator and investigational device, do not include zero.
- Number of flow-stop episodes will be analysed, in a generalized linear mixed model, with subject included as a random component. Evidence of superior effect will be concluded, if the lower 95% confidence limit of the risk ratio between comparator and investigational device, is more than 1.

The models will include following fixed effects.

- Visit (visit 1 and 2 of catheterisation)
- Device (comparator and investigational device)

The power for concluding superiority of the investigational device is at least 90% or higher.

11.2 Pass/fail criteria

To demonstrate superiority of the investigational device, the null hypothesis of the primary endpoints must be rejected, at a 5% significance (alpha 0.05).

The pass criteria for the study are based on the results from analysing the two primary endpoints in a hierarchical fashion: rejecting the null-hypothesis on the first endpoint (Residual urine at first flow-stop) before continuing to the second (Number of flow-stop episodes).

12 Data management

12.1 Data collection and data management

12.1.1 Data Collection in the clinical investigation

Data management and statistical analyses are carried out by the Medical Affairs, Coloplast A/S.

Data will be collected through an electronic data capturing (EDC) system on electronic Case Report Forms (eCRF), a secure, internet-based case report form. This system will be used to record all subject information collected in the investigation for secure data tracking and centralised data monitoring (“remote monitoring”) done by monitors, as defined in the monitoring plan.

The EDC system used is Rave EDC, version 2021.2.1, delivered by Medidata Solutions Inc. The system is designed to be compliant with the FDA requirements of 21 CFR part 11. It is a validated data management system allowing only qualified and trained personnel to enter the system. The system has full audit trail and electronic signature.

The sponsor will be responsible for training the investigator or delegate, in completion of the eCRF.

Principal Investigator, or delegate, at the clinical site will perform primary data collection directly into the eCRF or drawn from source-document reviews (according to the source data specification form). The eCRF will be completed on a continuous basis starting from the point of enrolling the subject to final follow up.

The eCRF will be completed by the investigator, or delegate, who have signed the Site Personnel Signature and Delegation List and Clinical Investigation Training Log. It will be the responsibility of the investigator to ensure that all measurements and observations are correctly noted in the eCRF.

All assessments and observations throughout the investigation for each subject must be carefully recorded in an eCRF during the visit or immediately after. The eCRF makes it possible to enter data right away when they are obtained. This is the preferred way of collecting data. In case this is not possible the data should be entered no later than 5 days after the visit / procedure.

Adverse events should be registered following the timelines described in the Adverse Event section.

In the unforeseen situation, where site cannot establish connection to the EDC system a paper CRF (pCRF) has been printed and supplied by sponsor in the Investigation Site File.

Raw data from the pressure sensor are stored in the electric boxes and copied on USB sticks. The USB sticks are sent to Coloplast A/S via courier. Raw data from either the USB sticks or the electric box are then analysed by two specialists independently.

A calibration/comparison is then performed between the two specialists and an excel sheet is made combining the relevant data. The excel sheet is thereby uploaded to an allocated SharePoint. Hereafter, the data derived from the catheterisation profile will be batch uploaded into the EDC system.

The site will complete a deviation eCRF form for all data-related deviations and all deviations that are not related to the data (for example, an untrained nurse performing study procedures) are reported by the monitor in the Site Report – Periodic Monitoring and actions are addressed to the Investigator for completion.

If any deviations to the investigation plan are detected during the monitoring visit, the Monitor shall ensure the site reports all deviations in the eCRF or on the Deviation log in the Investigator File. Additionally, the monitor must report any deviation noted during the visit in the Periodic Monitoring Report.

Monitor will align with data management in each investigation, how data management will be informed about all deviations.

The following information about the deviation will be collected:

- Site ID
- Subject ID
- Date the deviation took place
- What the deviation is related to
- If the deviation affects data integrity
- If the deviation affects subject safety
- Supplementary description of the deviation
- Actions taken with regards to the deviation

15 Device Accountability

All access to the investigational devices (including comparators) used in the clinical investigation is controlled by storage procedures and device accountability logs as described below. The investigational devices must only be used in this clinical investigation and only according to the CIP.

Sponsor keeps a device accountability log that states the physical location of all investigational devices from shipment of investigations devices to the investigational sites until return of or disposal.

The PI or an authorized designee keeps records documenting the receipt, use and return and disposal of the investigational devices, which includes:

- Date of receipt.
- Identification of each investigational device (batch no./serial no./unique code).
- The expire date,
- The date(s) of use.
- Subject identification.
- The date on which the investigational device was returned/explanted from the subject

The date of return unused, expired or malfunctioning investigational devices

16 Statement of compliance

The clinical investigation is conducted in accordance with:

- Ethical principles that have their origin in the Declaration of Helsinki, 1964, Last amended at the 59th WMA General Assembly, Brazil, October 2013.
- MDR (EU) 2017/745
- ISO 14155:2020 “Clinical Investigation of medical devices for human subjects – Good clinical practices”.
- Any applicable regional or national regulations will be specified in the country specific CIP.

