5.1 General

The investigation is a multi-centre, randomised, controlled crossover study including 42 male IC users.

The total study duration for the individual subject will be between 3 days to 2 weeks, consisting of three site visits. Visits 0 is an information visit and can be combined with V1 if subjects prefer. For visit 1 and 2, one catheterization will be performed in the hospital setting by a health care professional assessing flow stop episodes, bladder emptying and haematuria. Visit 2 can be performed the day after visit 1, or maximum 14 days after visit 1.

The study design and procedures are described below in Figure 5-1.

[figure not shown]

Figure 5-1 Study design

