5.2 Primary endpoints

- Number of flow-stop episodes derived from a catheterisation profile, [number].
- Residual volume at 1st flow-stop i.e., post catheterisation volume minus volume at 1st flow-stop, both derived from a catheterisation profile, [g].

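### The available text does not mask device when profiles are read for both primary endpoints or when data points are excluded, so unmasked judgement could favour the investigational device

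*Combined protocol and SAP*

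**What the plan says.** The title page describes an open-label randomised crossover, and section 5.1 gives 42 men.

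Section 5.2 takes both primary endpoints, the number of flow-stops and the residual volume at the first one, from the catheterisation profile. The second is defined as "Residual volume at 1st flow-stop i.e., post catheterisation volume minus volume at 1st flow-stop, both derived from a catheterisation profile, [g"].

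Under section 12.1.1 the sensor files go to the sponsor. Then "Raw data from either the USB sticks or the electric box are then analysed by two specialists independently", and "A calibration/comparison is then performed between the two specialists and an excel sheet is made combining the relevant data". The merged values are uploaded to the study database. No masking is described.

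Two other places involve site staff. Section 5.1 has "one catheterization will be performed in the hospital setting by a health care professional assessing flow stop episodes, bladder emptying and haematuria". The schedule table that follows section 7.1 lists "Urine volume at 1 st flow stop" against the investigator or delegate.

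On exclusions, section 10.2 states: "Individual endpoints/data points may be excluded from the analysis, even though the corresponding subject belongs to any of the pre-defined populations". The condition attached is "Exclusion of subjects or data points must be documented". The same section sets a review meeting before database lock, attended by at least the data manager, clinical manager and statistician, to classify subjects.

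Section 11.2 passes the study in a fixed order: "rejecting the null-hypothesis on the first endpoint (Residual urine at first flow-stop) before continuing to the second (Number of flow-stop episodes").

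**The concern.** Two readers and a comparison step suggest that identifying a flow-stop can call for judgement. The plan also states a direction in advance: the rationale for the haematuria measurement expects fewer mucosal suctions with the micro-hole catheter. A reader who knows the device may settle borderline traces in that direction without intending to. Double reading removes random error and one reader's quirks, but not a leaning that both share. Documentation makes an exclusion visible afterwards but does not make it neutral.

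The two primary endpoints are not independent protection. One extra stop called on a comparator profile always raises its count. It also raises its residual volume whenever it precedes the stop previously called first. The fixed sequence makes a false pass on both endpoints less likely, but it does nothing for the first test, which carries the first superiority claim.

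It is also not fully clear whose reading counts. If values assessed at the bedside could enter the primary analysis, masking the specialists would not be enough.

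**Working it through.** **No plan figure to reproduce.** The point concerns procedure. The available text gives no flow-stop rate, SD or reading-error rate, so every rate below is an assumption.

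**1. Direction.** Residual = drained volume − volume at first stop. Take 350 g drained and a first stop at 300 g, so the residual is 50 g.
- An extra call at 200 g gives 350 − 200 = 150 g, and the count rises by 1.
- An extra call at 320 g leaves 50 g, and the count rises by 1.
- With no stop called before (residual taken as 0), a call at 200 g moves it from 0 to 150 g.

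The residual can therefore rise or stay the same but never fall, and the count always rises.

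**2. General sensitivity.** Let b be a systematic bias in units of the SD of the within-subject difference, with no true effect. The chance of a false favourable result on one endpoint is P(T > 2.021), where T is noncentral t with 40 df and noncentrality b√42. For b = 0.10, the noncentrality is 0.10 × 6.481 = 0.648.

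| b | 0 | 0.05 | 0.10 | 0.20 | 0.30 |
|---|---|---|---|---|---|
| False favourable result | 2.5% | 5.0% | 9.2% | 24.4% | 47.5% |

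**3. Extra calls on comparator profiles.** 20,000 null trials were simulated per setting, with 21 subjects per sequence.
- Counts: Poisson with a shared subject gamma frailty (shape 1), mean 0.5, 1.0 or 1.5.
- Volume: lognormal, median 350 g, log-SD 0.3 between and 0.25 within subjects. Stops are uniform over drained volume.
- Test 1 (residual): visit-adjusted paired t, 40 df.
- Test 2 (count): ln(X_C/X_I) − 1.96·√(1/X_C + 1/X_I) > 0, where X_C and X_I are the total counts for comparator and investigational device.

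False-pass rates with extra calls placed uniformly:

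| Mean stops | Profiles with an extra call | Test 1 | Test 2 | Both |
|---|---|---|---|---|
| 0.5 | 0 | 2.4% | 2.3% | 0.8% |
| 0.5 | 10% | 7.7% | 8.2% | 3.4% |
| 0.5 | 20% | 17.8% | 21.0% | 10.5% |
| 1.0 | 0 | 2.4% | 2.2% | 0.5% |
| 1.0 | 10% | 5.7% | 6.2% | 1.9% |
| 1.0 | 20% | 11.6% | 13.1% | 4.9% |
| 1.5 | 0 | 2.5% | 2.4% | 0.5% |
| 1.5 | 10% | 5.3% | 5.7% | 1.4% |
| 1.5 | 20% | 9.6% | 10.6% | 3.4% |

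Frailty shape 2 is similar, with test 1 as low as about 8% at the 20% rate. If extra calls fall only in the last 30% of volume, test 1 is 3–4% (10% of profiles) or 3–5% (20%), and both tests 0.9–2.1% or 1.4–3.9%.

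**4. Selective exclusion.** There are 42 × 2 = 84 profiles. If 5% or 10% are doubtful (4.2 or 8.4) and only those unfavourable to the investigational device are dropped, about 2 or 4 values go. Unfavourable means an investigational value above the trial mean or a comparator value at or below it. Test 1 uses a REML random-intercept model with visit and device.

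| Mean stops | None dropped | 5% doubtful | 10% doubtful | All of the 10% dropped, whatever the device |
|---|---|---|---|---|
| 0.5 | 2.4% | 3.9% | 5.2% | 2.4% |
| 1.0 | 2.6% | 4.0% | 5.9% | 2.5% |
| 1.5 | 2.4% | 3.8% | 6.1% | 2.4% |

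A complete-pairs analysis gives slightly lower figures, 3.3–3.5% and 4.6–4.9%. In the last column the error rate stays at its nominal level, so the inflation comes from the link to device and not from dropping data.

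**The case against.** The strongest reply is that this argues from silence. Sections 5.4 and 5.7, most of 5.8, the start of section 10 and 11.1 are not shown, and the gap in 12.1.1 falls just after the reading paragraphs. Masking or a flow-stop rule may be written there. That stands: the point cannot be put as a plan without masking, only as one whose available text states none.

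A fixed numerical threshold for a flow-stop would remove most of the extra-call route. That also stands, though the two-reader comparison points towards some discretion.

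The simulated rates are stress cases. Every extra call goes against the comparator and survives both readings. With 5% of profiles affected, the first test is only about 3–5% and both tests about 1–2%. At 10%, a false pass on both (1.4–3.4%) is near the 2.5% nominal for a single test. This is fair for the overall pass, but section 10.4 allows a superiority conclusion for each endpoint, so the first-test figures still matter.

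The review meeting before lock is a real safeguard, but its stated task is classifying subjects and it is not said to be masked.

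The site-staff entries may simply record who performs the procedure, since the schedule names the investigator or delegate on every visible row. A small wording change would settle that.

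Finally, restricting exclusions to technical failures could bar others, such as use of the wrong device. Those are treatment deviations, for which section 10.2 already provides the per-protocol set.

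**Conclusion.** The concern holds as a point that should be addressed, with medium confidence. The study is open-label, both pass/fail endpoints depend on a reading made after the visit, and the available text masks neither that reading nor the exclusion of values. The direction of a shared bias follows from the endpoint definitions. Its size does not: it rests on assumed flow-stop rates, assumed rates of borderline calls and the premise that judgement is involved.

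On those assumptions the first test's false-pass rate goes from about 2.4% to between 3% and 8% when 10% of comparator profiles are affected, and to between 3% and 18% at 20%. The lower ends are for late calls and the upper for calls anywhere in drainage. Selective exclusion of about 2 to 4 values takes it to about 4–6%. Nothing here implies misconduct, and the documents do not say who employs the specialists.

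**What to change.** - **Section 12.1:** name the two specialists' reconciled reading as the only source of both primary endpoints. Supply the raw files to the same two specialists under a random code without device or visit. Lock the readings and the reconciliation before linking to the randomisation.
- **Sections 5.1 and 7.1 (schedule):** align the wording with 5.2, so that site staff record the profile and do not determine the primary endpoint values.
- **Section 10.2:** limit data-point exclusions from the full analysis set to technical failure of the sensor or file, decided on the coded file before linkage. Add a sensitivity analysis using all recorded values.
- **If masking is already stated in text not shown:** cross-reference it in 12.1 and 10.2.

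The cost is file coding by data management, one person to hold the key, and wording in four sections. It needs no extra readers and adds no burden for subjects. The limitation is that the shape of a profile may sometimes reveal the device, so masking would be imperfect.
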